1.1 Disease Background

Prostate cancer is the most commonly diagnosed non-cutaneous malignancy in men, with an estimated 180,000 cases annually in the United States [1]. It is the second most common cause of cancer mortality in the United States as well, with over 26,000 deaths in 2016 [1]. The discrepancy between the incidence and mortality numbers demonstrate its potential curability if treated while disease is local, as well as the non-lethal nature of some cancers, even if not treated definitively. While many men are cured of their disease, many others will unfortunately progress to incurable and lethal metastatic disease.

1.1.1. Clinical States of Prostate Cancer

The course of prostate cancer from diagnosis to death has been described as a series of distinct clinical states (See Figure 1.). These states are defined by the extent of disease and status of responsiveness to hormonal therapy. Therapies have been developed for specific states, as each state presents unique risks to the patient and different responsiveness of the disease to therapy.

[figure not shown]

Figure 1. Clinical states of prostate cancer [2]

1.1.2. The Biochemically Recurrent Disease State

For patients who have undergone definitive local therapy for prostate cancer, for example with a radical prostatectomy, the first signs of recurrent disease are biochemical in nature. For such a patient who develops detectable prostate specific antigen (PSA), defined as confirmed values ≥ 0.2 for patients s/p prostatectomy, the clinical state is known as biochemically recurrent prostate cancer [3]. This state is further characterized by the lack of evidence of metastatic prostate cancer on traditional imaging, including CT scans of the abdomen and pelvis and NM bone scans of the skeleton. Salvage radiation therapy is potentially curative in some patients with biochemical recurrence [4].

For patients who were not candidates for salvage radiation therapy or who experience a rising PSA despite that therapy, their natural history will vary significantly depending on the clinical characteristics of the cancer. The risk of development of metastasis (and thus potentially lethal prostate cancer) has been shown to be dependent on multiple longitudinal

clinical characteristics [5]. Two of these clinical criteria are Gleason score sum and rate of rise of the PSA—the PSA Doubling time (PSADT). Based upon registry data for hundreds of patients who were treated with radical prostatectomies for localized prostate cancer, and subsequently experienced biochemical recurrence, nomograms have been constructed regarding the risk of developing metastatic disease based upon the Gleason score and/or PSADT. One of the largest cohorts observed was the Johns Hopkins cohort, wherein patients with biochemical recurrence were observed (without hormonal therapy) until the development of radiographic or clinical metastasis, thus demonstrating the natural history of the disease [6].

1.1.3. High Risk Patients with Biochemically Recurrent Prostate Cancer by PSADT

In the Hopkins cohort of 450 patients, patients with PSADT > 9 months rarely developed metastasis in first 5-years of follow-up [6]. In fact, the median metastasis-free survival for patients with PSADT 9-15 months and PSADT >15 months was 13 and 15 years, respectively. On the other hand, patients with PSAT < 9 months did have significant risks for development of clinical metastasis. The median metastasis-free survival for patients with PSADT <3 months and 3-9 months was 1 and 4 years, respectively, with the vast majority of these patients developing clinical metastasis within 5 years of follow-up.

These numbers were further refined with a recent expanded analysis that was inclusive of the Hopkins cohort and Department of Defense's Center for Prostate Disease Research database, those patients with PSADT < 6 months truly represented the high risk group [7]. In that study, with PSADT of 3-6 months developed distant clinical metastasis with twice the risk compared to those with PSADT 6-9 months by 5 years. Patients with PSADT <3 months had an even higher risk development of metastasis (Hazard Ratio of 2.4 compared to the group with PSADT 6-9 months).

1.2 Treatment Background

1.2.1 Description and mechanism of action

PARP functions in the DNA repair pathway, specifically by serving in base excision repair of DNA single strand breaks. Inhibition of PARP results in inability for cells to repair single strand breaks. Cells normally would employ the error-free homologous recombination pathway to repair such defects. However, in tumors that harbor defects in these DNA repair genes (such as BRCA1/2), the strand breaks lead to chromosomal instability and eventually cell death [8]. Olaparib functions in cells to inhibit various isoforms of PARP.

Investigators should be familiar with the current olaparib (AZD2281) Investigator Brochure (IB).

Olaparib (AZD2281, KU-0059436) is a potent Polyadenosine 5'diphosphoribose [poly (ADP ribose)] polymerization (PARP) inhibitor (PARP-1, -2 and -3) that is being developed as an oral therapy, both as a monotherapy (including maintenance) and for combination with chemotherapy and other anti-cancer agents.

PARP inhibition is a novel approach to targeting tumors with deficiencies in DNA repair mechanisms. PARP enzymes are essential for repairing DNA single strand breaks (SSBs).

Inhibiting PARPs leads to the persistence of SSBs, which are then converted to the more serious DNA double strand breaks (DSBs) during the process of DNA replication. During the process of cell division, DSBs can be efficiently repaired in normal cells by homologous recombination repair (HR). Tumors with HR deficiencies (HRD), such as ovarian cancers in patients with BRCA1/2 mutations, cannot accurately repair the DNA damage, which may become lethal to cells as it accumulates. In such tumor types, olaparib may offer a potentially efficacious and less toxic cancer treatment compared with currently available chemotherapy regimens.

BRCA1 and BRCA2 defective tumors are intrinsically sensitive to PARP inhibitors, both in tumor models *in vivo* [9, 10] and in the clinic [11]. The mechanism of action for olaparib results from the trapping of inactive PARP onto the single-strand breaks preventing their repair [12, 13]. Persistence of SSBs during DNA replication results in their conversion into the more serious DNA DSBs that would normally be repaired by HR repair. Olaparib has been shown to inhibit selected tumor cell lines *in vitro* and in xenograft and primary explant models as well as in genetic BRCA knock-out models, either as a stand-alone treatment or in combination with established chemotherapies.

Olaparib is FDA-approved for the treatment of ovarian cancer patients who have progressed after three or more prior lines of therapy and harbor known or suspected deleterious mutations in BRCA1 or BRCA2 [14]. It has been studied in limited fashion in patients with advanced prostate cancer.

In addition to its efficacy in BRCA1 and BRCA2 defective tumors, Olaparib has been demonstrated to bind the PARP protein thus trapping it on DNA [13]. This other mechanism is believed to generate further cytotoxicity to cancer cells, as multiple other cellular pathways (beyond homologous recombination) are needed to remove the trapped protein and restore DNA integrity.

1.2.2 Preclinical Studies

The pre-clinical experience is fully described in the current version of the olaparib Investigator's Brochure (IB).

Olaparib has demonstrated *in vitro* and *in vivo* efficacy in preclinical studies in certain prostate cancer cell lines. The study of Brenner et al. tested VCaP cells *in vitro* and as xenografts and demonstrated efficacy of olaparib monotherapy compared to controls [15]. Efficacy in 22Rv1 cell line xenografts was similarly seen with olaparib in a separate study [16]. Other cell lines were not sensitive in preclinical studies. These included PC3 cells [15] and LNCaP cells [17].

1.2.3 Clinical Studies in Prostate Cancer

Clinical experience with olaparib is fully described in the current version of the olaparib Investigator's Brochure.

Small numbers of advanced prostate cancer patients were included in initial clinical studies of olaparib. In the initial phase I report on olaparib, 3 patients with prostate cancer were included [11]. In a follow-up study of patients with germline BRCA mutations, 8 prostate cancer patients were included [18].

Recently, a larger cohort of prostate cancer patients treated with olaparib was published [19]. Patients were treated with the FDA-approved dose of 400mg by mouth twice daily. In the trial, 50 patients were enrolled. Three patients discontinued olaparib due to adverse events. There were 30 adverse events of grade 3-4 level. Grade 3-4 events occurring in greater than 1 patient were anemia (20%), fatigue (12%), leukopenia (6%), neutropenia and thrombocytopenia (4%).

Of the patients in the study, 16 were identified to have a mutation in DNA repair genes (BRCA1, BRCA2, ATM, FANCA, CHEK2, PALB2, HDAC2, RAD51, MLH3, ERCC3, MRE11, or NBN) [19]. Eleven of 49 evaluable patients experienced a greater than 50% decline in PSA (a PSA50 response). Six patients achieved a partial radiographic response by RECIST criteria. Every patient with a radiographic response also had a PSA50 response. Of these 11 responders in the study, 10 were among the patients with the mutations in the tested DNA repair genes. One responder was among the remaining 33 without an identified mutations.

There are currently no studies published in hormone sensitive prostate cancer patients.

1.2.4 Clinical Studies in All Diseases

The toxicology and safety pharmacology is fully described in the current version of the olaparib Investigator's Brochure (IB).

The largest pool of data for olaparib is drawn from a phase II trial of patients with germline delirious BRCA 1 or 2 mutations [18]. That study included 298 patients, including 193 with ovarian cancer and 62 with breast cancer. The analysis of the ovarian cancer cohort in this study led to the FDA-approval of olaparib. The overall tumor response rate by RECIST criteria was 26.2% across all tumor types. Specifically for the ovarian cancer cohort, the median response duration was 7.9 months.

Adverse events were reported in the trial and are summarized below:

Adverse Event	Any Grade Toxicity	Grade 3-4 Toxicity
Fatigue	59.1%	6.4
Nausea	59.1%	0.3
Vomiting	37.2%	2.3
Anemia	32.9%	17.4
Diarrhea	27.2%	1.3
Abdominal Pain	25.8%	5.7
Decreased Appetite	20.8%	0.3
Dyspepsia	17.4%	0.0
Headache	16.1%	0.3
Dysgeusia	15.8%	0.0

Table 1. Events occurring in >15% (any grade) or >5% (grade 3-4) in the trial [18].

Severe rare but serious adverse events have been cataloged in clinical trials to this point. In the Kaufman study, 6 (2%) of patients developed myelodysplastic syndrome or acute myeloid leukemia. Of all 2618 patients treated with olaparib on clinical trials, 22 (<1%) developed MDS or AML; however, the occurrence was fatal in most cases (per the investigators brochure). Pneumonitis also was seen to occur in <1% of patients.

1.3 Rationale for olaparib in high risk biochemically recurrent prostate cancer

1.3.1 DNA repair defects are common in prostate cancer

Several large studies have been recently published cataloging the genetic mutations that are present in prostate cancer. The TCGA examined 333 primary prostatectomy specimens that were collected without selection for risk group or Gleason grade [20]. In that analysis, inactivating mutations in DNA repair genes were identified in 19% of samples. By prevalence, these genes identified were FANCD2 (7%), ATM (4%), BRCA2 (3%), RAD51C (3%), CDK12 (2%), and BRCA1 (1%). Specifically looking at the genes identified in the Mateo study (BRCA1, BRCA2, ATM, FANCA, CHEK2, PALB2, HDAC2, RAD51, MLH3, ERCC3, MRE11A, NBN) [19], the prevalence was 9%.

A similar analysis of the genetic mutations was performed in a cohort of 150 samples from patients with metastatic castration-resistant prostate cancer [21]. In that study, the authors identified 23% of patients harbored mutations in DNA repair genes. Most frequently mutated DNA repair genes were BRCA2 (13.3%), ATM (7.3%), and CDK12 (4.7%). Again using the Mateo study's list of genes, the prevalence of mutations was 18%.

A final study to discuss regarding the prevalence of DNA repair defects in prostate cancer is a recent analysis of the prevalence of germline mutations in patients with prostate cancer [22]. That study examined 692 patients with metastatic prostate cancer and tested for germline mutations in 20 DNA repair genes. Overall 11.8% of patients were found to have germline DNA repair mutations. The most commonly mutated genes were BRCA2 (5.3%), CHEK2 (1.9%), ATM (1.6%), BRCA1 (0.9%), RAD51D (0.4%), and PALB2 (0.4%). The authors compared the frequencies of mutations to those present in 499 with localized prostate cancer. In the localized prostate cancer cohort, the prevalence was lower at 4.6%. Of note, the baseline prevalence for these mutations in the general population is 2.7%.

These studies demonstrate that DNA repair mutations are relatively common in prostate cancer, and are more common in metastatic prostate cancer than in localized prostate cancer. Based upon these large genomic analyses for cohorts of patients with prostate cancer, we establish a range of likely prevalence for DNA repair defective tumors for patients with biochemically recurrent prostate cancer. For mutations detectable in tumor tissue, the prevalence for biochemically recurrent patients likely falls between the 19-23% range per TCGA and SU2C data (9-18% for those genes from the Mateo study). The anticipated range for germline mutations is 4.6-11.8% per the Prichard analysis.

Yet, despite some encouraging preliminary data on a mutation signature that is predictive of response to olaparib, the optimal biomarker profile for response is probably not known at this time. This is in fact demonstrated in the Mateo study, in which one patient without a known genetic defect in the analyzed genes achieved an 88% PSA response, a partial response per RECIST criteria, and a duration of response of at least 44 weeks at the time of publication.

1.3.2 Rationale for conducting study

There are several pending trials are being conducted with olaparib for patients with metastatic CRPC, including olaparib as monotherapy (NCT01682772) and olaparib in combination with enzalutamide (NCT02500901). The FDA recently announced breakthrough designation for olaparib for metastatic CRPC, refractory to novel hormone

therapy and chemotherapy, with mutations in BRCA1, BRCA2, or ATM. While PARP inhibition is showing promise in these initial studies, reserving its use for end-stage patients may not be the optimal timing for olaparib therapy in some patients. PARP inhibition has not been tested in earlier disease states for prostate cancer.

Olaparib may be an ideal therapy for men with biochemically recurrent prostate cancer. PARP inhibition with olaparib in this earlier disease state may be more effective in hormone-sensitive prostate cancer (rather than in heavily pre-treated/resistant tumors), as tumor heterogeneity may be significantly lower. In addition, it is unknown whether genetic changes identified in prostatectomy specimens will be predictive of response to olaparib. PARP inhibition may also be active in ways beyond the DNA repair pathway for prostate cancer. This trial will attempt to test questions regarding the activity of olaparib in hormone-naïve prostate cancer and explore associations between responses with genetic mutations and expression profiles identified in the primary prostatectomy specimens.

In this trial, subjects will be enrolled with biochemically recurrent prostate cancer. Patients will be required to have undergone prior definitive radical prostatectomy with tissue available for analysis. Patients will also have required to have previously been treated with salvage radiation therapy, declined salvage radiation therapy, or were not candidates for salvage radiation. By requiring prior definitive therapy and attempted salvage therapy, the enrolled patients are those that are not felt to have known curative options remaining for their cancer.

Furthermore, patients are required to have high risk for development of metastatic disease, specifically by requiring a PSADT < 6 months. This selects for patients who have a high risk of suffering morbidity and mortality from prostate cancer in the future. Given the potential toxicity of any treatment in this space, weighing that risk with a potential benefit is important and thus is the rationale for limiting enrollment to those patients with rapid PSADT.

The current standard of care treatments for patients with high risk biochemically recurrent prostate cancer are either observation or ADT [23]. ADT has not been shown to provide a survival benefit in this setting, and the decision to initiate ADT will depend on patient preference and perceived risks of the disease. A non-hormonal therapy such as olaparib would provide an alternative to ADT as a potential treatment option for these patients.

The study is an open-label single arm phase II study. Enrolled subjects will be treated with olaparib 300mg by mouth twice daily until progression or toxicity requiring cessation. Patients will be assessed at least monthly for toxicity, including laboratory investigations. Because an alternative standard approach for these patients is observation (and continued PSA rise with a similar doubling time in >95% of patients), an inactive compound in this space would be expected to provide a 5% or less response rate, which would be the same as observation for these patients. It is in that context that a single arm study is being conducted rather than randomized placebo-controlled study. Among data to be collected include monthly PSA values, toxicity assessments, duration of olaparib therapy, and correlative investigations. The correlative studies include multiple studies using tumor tissue from the explanted prostate tumors: genomic mutation analysis, RNA expression profiling, and baseline PARP-1 and γH2AX protein levels.

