An enriched population will be required to have a known/suspected deleterious mutation in of the genes listed above. The data for the enriched population will be analyzed separately from the data in the first (and second, if applicable) stage(s). The assumptions for the enriched population: null hypothesis of 0.3 PSA response rate, and alternative hypothesis of 0.6 for the biomarker selected population. The sample size for the selected population is 20 subjects. If ≥ 10 respond, the null is rejected for the biomarker selected population and efficacy will be concluded for the biomarker subgroup.

This design will have power for detecting an effect in the unselected population of 0.90-0.91 and a power for detecting an effect in the selected population (if there is no effect in the unselected) of 0.79-0.80, with an overall type I error 0.1-0.11, assuming the biomarker prevalence 10-15%, based upon 10,000 simulations of possible outcomes.

Schema:

Number of Patients: 50.

Our institution has a record of accruing 1-2 patients per month to trials in patients with biochemically recurrent prostate cancer with similar inclusion criteria. With opening at multiple sites, trial would be expected to fully accrue in 24 months or less. The primary endpoint is expected to be reportable within 30 months, or sooner, after trial activation.

Main Eligibility Criteria:

Inclusion:

1. Histologic diagnosis of adenocarcinoma of the prostate.
2. Prior local therapy with prostatectomy required, with available tissue from prostatectomy specimen to send for genomic and transcriptomic testing.
3. Prior salvage or adjuvant radiation therapy is allowed but not mandated. Radiation therapy must have been completed for at least 6 months.
4. Absolute PSA ≥ 1 ng/ml. Prior undetectable PSA post-prostatectomy is not required.
5. PSADT ≤ 6 months, based upon ≥ 3 consecutive measurements collected in the past 12 months, at least 4 weeks apart, calculated using MSKCC calculator
6. No radiographic evidence of metastatic disease by CT scan and bone scan, performed within the prior 4 weeks.
7. Serum testosterone ≥ 150 ng/dl.
8. Participants must have normal organ and bone marrow function measured within 28 days prior to administration of study treatment as defined below:
 - Hemoglobin ≥ 10.0 g/dL with no blood transfusion in the past 28 days
 - Absolute neutrophil count (ANC) $\geq 1.5 \times 10^9$ /L
 - Platelet count $\geq 75 \times 10^9$ /L

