3. PATIENT SELECTION

3.1 Target Population

The target population is men with prostate cancer who have experienced a rising PSA (biochemical recurrence) after definitive local therapy with a radical prostatectomy. This population will not have evidence of metastatic disease on CT scan and NM bone scan. Furthermore, the population will be high risk for development of metastatic disease, as defined by a PSA doubling time (PSADT) of < 6 months and an absolute PSA value of ≥1.0 ng/ml.

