4.1.1 Registration at Johns Hopkins

Confirm eligibility as defined in **Section**

- *(if an enriched population is not accrued)* To estimate PSA50 response in “biomarker positive” patients, based upon FoundationOne tissue-based mutations in the pre-specified gene list (ATM, BARD1, BRCA1, BRCA2, BRIP1, CDK12, CHEK1, CHEK2, FANCL, PALB2, PPP2R2A, RAD51B, RAD51C, RAD51D, or other DNA repair genes).

- (if an enriched population is not accrued) To estimate PSA50 response in “biomarker negative” patients, based upon tissue-based mutations in the pre-specified gene list.
- To estimate PSA50 response rate for patients with and without a mutation on the pre-specified list, based upon plasma cell-free DNA analysis using the pre-specified gene list.
- To develop a genetic mutation signature associated with response to olaparib. For this objective, the biomarker signature will not be defined *a priori* but instead this will involve an exploratory analysis.
- To develop an RNA expression signature associated with response to olaparib.
- To investigate any association between PARP-1 and γ H2AX protein levels in tumor with response to olaparib.
- To estimate median metastasis-free survival.
- To estimate median time to next anti-cancer therapy.

3. Patient Selection.

Obtain informed consent, by following procedures in **Section 11.3 Written Informed Consent.**

Patient will be entered into CRMS system and enrolled in trial.

4.1.2 *Multicenter/Participating site registration*

Central registration for this study will take place at Johns Hopkins.

Patient registration at each study site/institution will be conducted according to the institution’s established policies. Before registration, patients will be asked to sign and date an Institutional Review Board (IRB)-approved consent form and a research authorization/HIPAA form. Patients must be registered with their local site/institution and also with the sponsor or Lead Site before beginning any treatment or study activities.

5. **TREATMENT/INTERVENTION PLAN**

The following assessments and procedures will occur during the study. A schedule of assessments is provided in Table 2.

Table 2 Study Calendar

	Prestudy	Study Period				
		On Treatment Assessments (Every 28 days)				Off Treatment / Follow-up
		Day -7 ^{a,h} (±7days)	C1D1 ^{d,h} (±3 d)	C2D1 ^{d,h} (±3 d)	C3D1 ^h (±3 d)	CnD1 ^h (±3 d)
Informed consent	X					
Demographics	X					
Complete Medical history	X					
EKG	X					
Interval Medical history		X	X	X	X	X

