5.1 Screening/Pretreatment Assessment (Day -7 ±7 days)

Before initiating any screening activities, the scope of the study should be explained to each patient. Patients should be advised of any known risks inherent in the planned procedures, any alternative treatment options, their right to withdraw from the study at any time for any reason, and their right to privacy. After this explanation, patients should be asked to sign and date a Notice of Privacy Practice research authorization/HIPAA form and an IRB-approved statement of informed consent that meets the requirements of the Code of Federal Regulations (Federal Register Vol. 46, No. 17, January 27, 1981, part 50).

- The screening visit will determine patient eligibility according to the inclusion and exclusion criteria (Sections 3.3 Inclusion Criteria & Histological proof of adenocarcinoma of the prostate)
- Prior local therapy with prostatectomy required, with available tissue from prostatectomy specimen to send for genomic and transcriptomic testing. Specifically, either FFPE blocks or 35-40 unstained slides from the primary prostatectomy specimen will need to be available for central pathologic review and processing.
- Prior salvage or adjuvant radiation therapy is allowed but not mandated. Radiation therapy must have been completed for at least 6 months.
- Absolute PSA ≥ 1 ng/ml. Prior undetectable PSA post-prostatectomy is not required.
- PSADT ≤ 6 months, based upon ≥ 3 consecutive measurements collected in the past 12 months, at least 4 weeks apart, calculating using the MSKCC calculator (<https://www.mskcc.org/nomograms/prostate/psa-doubling-time>)
- No radiographic evidence of metastatic disease by CT scan and bone scan, performed within the prior 4 weeks.
- Serum testosterone ≥ 150 ng/dl.
- Participants must have normal organ and bone marrow function measured within 28 days prior to administration of study treatment as defined below:
 - Hemoglobin ≥ 10.0 g/dL with no blood transfusion in the past 28 days
 - Absolute neutrophil count (ANC) $\geq 1.5 \times 10^9/L$
 - Platelet count $\geq 75 \times 10^9/L$
 - Total bilirubin $\leq 1.5 \times$ institutional upper limit of normal (ULN)
 - Aspartate aminotransferase (AST) (Serum Glutamic Oxaloacetic Transaminase (SGOT)) / Alanine aminotransferase (ALT) (Serum Glutamic Pyruvate Transaminase (SGPT)) $< 2.5 \times$ institutional upper limit of normal

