Note: Patients with elevations in bilirubin, AST, or ALT should be thoroughly evaluated for the etiology of this abnormality prior to entry and patients with evidence of viral infection should be excluded.

- Participants must have creatinine clearance estimated using the Cockcroft-Gault equation of ≥ 51 mL/min:

$$\text{Estimated creatinine clearance} = \frac{(140 - \text{age [years]}) \times \text{weight (kg)}}{\text{serum creatinine (mg/dL)} \times 72}$$

Note: Patients with creatinine clearance between 51- 80 mL/min either at trial enrolment or during the course of the trial should be monitored every 2 weeks for laboratory assessment and toxicity evaluation.

- ECOG PS \leq 1. (Appendix A: Performance Status Criteria)
- Participants must have a life expectancy \geq 16 weeks.
- Male participants and their partners, who are sexually active and of childbearing potential, must agree to the use of two highly effective forms of contraception in combination [see appendix E for acceptable methods], throughout the period of taking study treatment and for 3 months after last dose of study drug to prevent pregnancy in a partner.
- *For enrichment stage of trial only (if necessary):* Confirmation of a suspected/known deleterious mutation in a gene of interest (ATM, BARD1, BRCA1, BRCA2, BRIP1, CDK12, CHEK1, CHEK2, FANCL, PALB2, PPP2R2A, RAD51B, RAD51C, RAD51D or other DNA repair genes) via CLIA certified testing.

3.4 Exclusion Criteria). The following assessments will be performed at this visit:

- obtain informed consent and research authorization
- record demographics (including age) and medical history (including prior treatment for prostate carcinoma)
- conduct physical exam (including vital signs, height/weight)
- obtain history regarding prior treatment history for prostate cancer (including history of ADT, history of radiation therapy or other local therapy, and prior PSA history to calculate PSADT).
- obtain histologic confirmation of disease, and radiographic evidence of lack of metastatic disease. If radiographic studies have not been performed in prior 4 weeks, they must be obtained as part of screening.
- perform laboratory tests: Complete blood count w/Diff, PSA, Comprehensive metabolic panel, urinalysis, PT/INR, PTT, testosterone.
- PSA doubling time will be confirmed using MSKCC calculator (<https://www.mskcc.org/nomograms/prostate/psa-doubling-time>)
- assess performance status (ECOG). (Appendix A)

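### The three salvage-radiotherapy routes that Section 1.3.2 requires appear in no eligibility criterion, so a radiotherapy-naive man who is still a candidate and has not declined can be enrolled

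*Combined protocol and SAP*

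**What the plan says.** Section 1.3.2 sets a requirement. Besides prior prostatectomy, men must have "previously been treated with salvage radiation therapy, declined salvage radiation therapy, or were not candidates for salvage radiation". It then gives the purpose: "By requiring prior definitive therapy and attempted salvage therapy, the enrolled patients are those that are not felt to have known curative options remaining". Section 1.1.2 supplies the background, describing salvage radiotherapy as able to cure some men with biochemical recurrence.

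Eligibility is decided elsewhere. Section 4.1.1 instructs the lead center to "Confirm eligibility as defined in" the patient-selection section. Section 5.1 states: "The screening visit will determine patient eligibility according to the inclusion and exclusion criteria". The texts they rely on say the following:

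- Section 3.1 describes men "who have experienced a rising PSA (biochemical recurrence) after definitive local therapy with a radical prostatectomy", without metastases on imaging and at high risk by PSADT and PSA. It does not mention salvage radiotherapy.
- The synopsis inclusion list, Section 3.3 and Section 5.1 all say "Prior salvage or adjuvant radiation therapy is allowed but not mandated", and add that any radiotherapy must have ended at least 6 months earlier.
- The exclusions in Section 3.4 and in the synopsis do not mention radiotherapy candidacy or refusal.
- Screening takes the treatment history, "including history of ADT, history of radiation therapy or other local therapy, and prior PSA history to calculate PSADT".

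On consent, Section 5.1 states: "Patients should be advised of any known risks inherent in the planned procedures, any alternative treatment options". Section 11.3 requires the alternatives to be reviewed and the form to list available standard therapies. Its examples are hormone treatment, chemotherapy and supportive care.

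**The concern.** A requirement stated in the rationale protects no one unless a criterion applies it. The protocol tells its readers that enrolled men have no known curative option left, and the three routes are how it supports that statement. If the criteria do not ask about the routes, a site can follow Section 3 to the letter and still enrol a man for whom salvage radiotherapy remains open and was never discussed.

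Two things are at stake. One is assurance that a treatment the protocol itself regards as curative for some men was considered before an investigational drug was started. The other is an accurate description of who was studied.

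**Working it through.** No arithmetic applies. The check is to take one hypothetical man through each text.

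**The man.** He has had a prostatectomy and tissue is available. His PSA is at least 1 ng/ml, his PSADT is at most 6 months, CT and bone scan are negative, and testosterone is at least 150 ng/dl. He meets all other criteria. He has never had radiotherapy, is still a candidate for salvage radiotherapy, and has not declined it.

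| Text | What it asks about radiotherapy | Result |
|---|---|---|
| 1.3.2 | Salvage radiotherapy given, declined, or not a candidate | Fails all three routes |
| 3.1 Target Population | Nothing | Passes |
| 3.3 Inclusion | Optional; 6-month interval if given | Passes; the interval does not apply |
| 3.4 Exclusion | Nothing on candidacy or refusal | No exclusion triggered |
| Synopsis criteria | Same as 3.3 and 3.4 on this point | Passes |
| 4.1.1 Registration | Refers to Section 3 | Passes |
| 5.1 Screening | Repeats 3.3; takes radiotherapy history | Passes |

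The 5.1 list should not be counted as independent evidence. It reads as a cross-reference to 3.3 that expanded into pasted text, so it is one omission carried forward.

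**Is "Prior salvage or adjuvant radiation therapy is allowed but not mandated" a contradiction of 1.3.2?** No. Section 1.3.2 also admits men who had no salvage radiotherapy, provided that they declined it or were not candidates. The two statements are compatible. The defect is that the condition attached to radiotherapy-naive men is missing from the criteria.

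**Does screening catch him?** The history item would show that he had no radiotherapy. Nothing says that the reason must be recorded, and the reason is what separates an eligible man from an ineligible one under 1.3.2.

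**Does consent catch him?** In part. Sections 5.1 and 11.3 create a general duty to discuss alternatives. But the examples in 11.3 leave out salvage radiotherapy. The synopsis (Concept and Rationale; Patient Acceptability/Ethics and Consent Issues) and Section 1.3.2 name the standard options for this population only as ADT or surveillance/observation. A discussion built on those passages could omit salvage radiotherapy without departing from any specific instruction.

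**The case against.** The strongest reply is that consent already does the work. Patients must be told of alternatives before any screening activity, and the examples in 11.3 are introduced as examples. A candidate who is told of salvage radiotherapy and chooses olaparib has in substance declined it, and so satisfies 1.3.2. A candidate who was not told was arguably consented contrary to 5.1 and 11.3. This has force and is one reason the severity is low. It does not close the gap, because a man can decline only an option put to him, and no text specifically requires that salvage radiotherapy be raised.

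It is also fair to say that 1.3.2 does not itself ask for documentation, so recording the reason goes a step beyond the protocol's own words. That step is justified only because it is cheap and makes the requirement verifiable.

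The case report forms and the consent form are not available for this review. Either may already cover the point, and the history item in 5.1 is not an exhaustive list. Nothing here should be read as a statement about what those forms contain.

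Finally, the phrase in 1.3.2 about attempted salvage therapy fits poorly with men who declined it. That is a loose summary in background text and changes no procedure.

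**Conclusion.** The point holds as a low-severity gap between the rationale and the eligibility criteria. As written, the criteria admit one kind of man whom 1.3.2 says is not enrolled: radiotherapy-naive, still a candidate for salvage radiotherapy, and not having declined it. The conclusion rests on the protocol text alone and assumes that sites apply the listed criteria as written.

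Its size cannot be stated in numbers, because the documents do not give the number of such men. Three stronger readings are tempting and are not supported:

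- *Men would lose a chance of cure.* Section 1.1.2 speaks of biochemical recurrence in general. The documents do not say whether salvage radiotherapy can cure at PSA of at least 1 ng/ml with PSADT of at most 6 months. Section 5.9 bars radiotherapy while a man is receiving olaparib, but 5.5.2.3 provides for stopping the drug before radiation and 6.4 lets a patient stop at any time. Enrolment may delay the option; it does not remove it.
- *The risk-benefit argument fails.* The explicit justification for accepting toxicity, in the synopsis and 1.3.2, rests on high risk and rapid PSADT.
- *The efficacy result is compromised.* The sample size, decision rules and interpretation of PSA50 response are unaffected.

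**What to change.** Add one criterion to Section 3.3 and the synopsis, and to the copy in 5.1: prior salvage radiotherapy, or not a candidate for it (including because of prior adjuvant radiotherapy), or declined it after discussion. Record at screening which route applies and, for a radiotherapy-naive man, the reason he had no salvage radiotherapy. Name salvage radiotherapy among the example alternatives in Section 11.3.

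The cost is one sentence in three places, one screening item and a few words in 11.3. The downside is slightly more screening work and possibly a few men excluded or delayed while the discussion takes place.
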